5.5. Analysis Plan

The primary analysis will be performed using the intention-to-treat principle so that all randomized patients will be included in the analysis. The t-test or the Mann-Whitney test will be used if the t-test assumptions are violated. Secondary endpoints of subjective comprehension, anxiety, satisfaction, and information location will be analyzed with the Mann-Whitney test. The binary outcome of consent rates will be compared using the Fisher exact test. The above unadjusted analyses will be complemented by analyses that adjust for potentially confounding

variables in regression analyses. Generalized estimating equations (GEE)⁵⁰ will be used to control for effect of confounding variables (e.g., patient demographics, health literacy level, strata) and a potential consenter effect (as more than one clinician could be involved in the consent process at a clinical trial site). GEE with identity link will be used for comprehension, anxiety and satisfaction analyses. Information location will be analyzed with LOG link and LOGIT link with accrual outcome. Variance will be estimated with the sandwich estimator if the number of consenters is > 30; otherwise the “leave-one-consenter-out” jackknife variance estimation will be used.⁵¹ Exact logistic regression will be used with accrual if the problem of small counts appears. Otherwise Wald tests will be used for significance testing. All two-way interactions between the group indicator (ETRIC vs. standard) and confounding variables will be tested and added to the model if significant. It is expected that all confounders will be analyzed as fixed effects except for the consenter which will be the repeated factor in the GEE. The form of continuous predictors will be either linear, quadratic, or categorized depending on the number of clusters observed in the dataset. Every category in categorical variables will have at least 10 subjects otherwise we will consider merging with neighboring categories. The presence of missing data in excess of 10% will be addressed by developing an imputation model for missing components given the observed part. Then, the multiple imputations approach will be used to estimate regression parameters and their standard errors.⁵²

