BMT CTN #1205 Statistical Analysis Plan (SAP)

Drafted by: [name] on 9/17/16

PROTOCOL: Easy-to-Read Informed Consent (ETRIC) for Hematopoietic Cell Transplantation Clinical Trials

Protocol Synopsis:

The BMT CTN protocol #1205 titled “Easy-to-Read Informed Consent (ETRIC) for Hematopoietic Cell Transplantation Clinical Trials” is a randomized, multicenter, prospective comparative study of ETRIC or standard consent form to improve patient comprehension of BMT CTN parent clinical trials. The primary objective is to compare objective comprehension scores on the Quality of Informed Consent (part A) instrument between patients randomized to the ETRIC versus the standard consent arms. Secondary objectives are to compare the following measures between the two arms: (1) subjective comprehension scores on the Quality of Informed Consent (part B) instrument and the modified Deaconess Informed Consent Comprehension Test instrument, (2) state anxiety scores on State Trait Anxiety Inventory instrument, (3) satisfaction score, (4) time taken for information location, and (5) patient consent rates on parent clinical trials. Per the original study design, the target sample size was 160 patients with 80 on each arm ensuring 64 patients per arm to complete Quality of Informed Consent part A comprehension survey. An interim analysis revealed that the survey completion rate was lower than expected, and then the target sample size was increased to 198 with expected 99 patients per group and 64 per arm to complete the Quality of Informed Consent part A questionnaire.

Study Status and Publication Plan:

The study opened enrollment in November 2013 and closed in August 2016 when the targeted sample of 198 patients was enrolled. Two manuscripts are anticipated from this trial. The first manuscript will describe the qualitative study and will detail the barriers and facilitators that were identified on semi-structured interviews of participating site research and IRB personnel. The analysis for this manuscript has been completed. The second manuscript will present the analysis of the randomized study that is detailed in this statistical analysis plan. We plan to circulate the first draft of the manuscript to the protocol team for review within 6 weeks after the analysis has been reviewed.

Survey instrument scoring:

- The Quality of Informed Consent Parts A and B will be scored as described in (Joffe et al, 2001)

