- The Rapid Estimate of Adult Literacy Revised (REALM-R, a health literacy measure) will be scored as described in (Bass et all, 2003): words “fat”, “flu”, and “pill” will not be scored.
- The New Vital Sign (a health literacy measure) will be scored as described in (Weiss et al, 2005)
- The State-Trait Anxiety Inventory (STAI) will be scores as described in its manual (Spielberger et al, 1983)

NCT02081248

- The Consent Form Satisfaction Survey will be summarized by its total score as the sum of responses to its seven Likert questions (0-4).
- The Deaconess Informed Consent Comprehension Test will be scored as described in (Miller et al, 1996). The total score ranges between 0-28.

Primary Endpoint and Data Analysis:

The primary endpoint of BMT CTB 1205 is the mean comprehension score on the Quality of Informed Consent (part A) instrument.

The primary analysis will be performed using all patients who completed the Quality of Informed Consent (Part A) and will be based on the two sample t-test or, if the t-test assumptions are violated, with Mann-Whitney test. The statistical significance will be declared if the P-values of a two-sided test <0.05 .

The following non-primary analyses will use all randomized patients with possible exclusion of clinical trials protocols with high missing data rates. Non-primary analysis will rely on linear regression models with multiple imputations to address missing data issues.

Analysis of interactions between the randomized assignment and (1) the trial protocol, (2) literacy level (REALM-R), (3) income, (4) age groups, (5) education level. The statistical significance of interactions will be declared at ALPHA 0.01 (Bonferroni adjustment for 5 tests). If the interaction test is significant then post-hoc comparisons between the ETRIC and standard consent groups will be performed for each level of a categorical variable.

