Data preparation: We will investigate functional forms of continuous predictor variables, such as "literacy level" (assessed via NVS or REALM-R) and "age" and the use of appropriate transformations of continuous predictors to make the associations with the outcome more linear and the distributions of model residuals closer to normal. We will also consider grouping continuous variables into three categories by tertiles if the linear association with the outcomes is not adequate. The categories of variables with multiple levels, such as "Education level" or "Income", will be grouped into wider categories.

The adjusted analysis of the primary endpoint will be based on the linear regression model. Potential confounding variables to include in the model are (1) the trial protocol, (2) literacy level (NVS or REALM-R, whichever is more predictive), (3) income, (4) gender, (5) age, (6) categorized race (WHITE vs OTHER). Forward stepwise variable selection will be used to find a parsimonious linear regression model with significant at ALPHA = 5% predictors.

Missing data: Since only near two thirds of all study participants are expected to complete the Quality of Informed Consent (Part A) questionnaire, we will develop an imputation model and use multiple imputations to fill-in missing values. The imputation model will use the information at baseline when the participant is enrolled into the study. Then, we will use Little and Rubin's approach (Little & Rubin, 2002) to combine the results of multiple imputations for estimating model parameters, variance covariance matrices, and P-values. To investigate the possibility of missing data which are not missing at random (NMAR), we will use tipping-point

NCT02081248

approach and find the ranges of the imputation model parameters when the inference on the effect of ETRIC consent does not change.

Dependence within data: The linear mixed models will be used to explore whether there is a need to control for clinical trial site or clinical trial site by protocol, both or neither.

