Alternative analyses: To satisfy model assumptions we will consider the use of monotone variance-stabilizing transformations for continuous variables. If, however, the model specification continuous being inadequate (non-Gaussian distribution of model residuals, outliers, etc.), we proceed with generalized estimating equations (GEE) instead of the mean linear regression. To accommodate potential dependence of responses within clinical trial sites “leave-one-site-out” cross-validation will be used to estimate robust standard errors of the test statistic (the regression coefficient of the ETRIC effect in either mean or median regression models).

Secondary Endpoints and Final Analysis:

Secondary continuous endpoints are subjective comprehension, anxiety, satisfaction, and information location. The only secondary binary endpoint is the consent rate for the parent clinical trial.

Analysis of secondary endpoints: By analogy with the primary endpoint, the secondary endpoints (1) subjective comprehension scores on the Quality of Informed Consent (part B) instrument, (2) the modified Deaconess Informed Consent Comprehension Test instrument, (3) state anxiety scores on State Trait Anxiety Inventory instrument, (4) overall satisfaction score will be analyzed using t- or Mann-Whitney tests as appropriate. The analysis of time to information location will be performed with generalized linear models (GLM) models using the LOG link function if nonlinearity needs to be accounted for. The comparison of consent rates between ETRIC and standard consent forms will be performed with GEE using the LOGIT link. The GEE model will control for the fixed effect of trial protocol and for the dependence within the clinical trial site. The statistical significance of the ETRIC intervention on each of the secondary endpoints will be declared if the P-values of two-sided Wald test with robust standard errors <0.05. Missing data will be treated by analogy with the primary outcome using multiple imputations and tipping-point analysis.

Patients to Include:

All patients who completed the Quality of Informed Consent (part A) survey will be included in the primary data analysis. All enrolled patients will be included in the data analysis of secondary endpoints.

Content of Tables

Tables:

Table 1: Demographics and baseline characteristics by treatment arm

Table 2: Study endpoints by treatment arm

Table 3: Interaction analyses for the Quality of Informed Consent (part A)

NCT02081248

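### The protocol sets an intention-to-treat primary analysis; the SAP runs it on QuIC Part A completers without declaring the change, and lets the imputed analyses drop whole parent protocols

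*SAP*

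**What the plan says.** **Protocol.** Section 5.5 states: "The primary analysis will be performed using the intention-to-treat principle so that all randomized patients will be included in the analysis". It adds that missing data above 10% will be handled by multiple imputation, which it ties to estimating regression parameters. Section 5.1 commits to analysing patients who joined 1205 before parent trials 0901 and 1203 closed. Section 4.1 removes from 1205, without assessments, anyone found ineligible for the parent trial before its consent discussion.

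**SAP.** Primary Endpoint and Data Analysis says "The primary analysis will be performed using all patients who completed the Quality of Informed Consent (Part A"), and Patients to Include repeats it: "All patients who completed the Quality of Informed Consent (part A) survey will be included in the primary data analysis". The Protocol Synopsis expects 99 patients per group and "64 per arm to complete the Quality of Informed Consent part A questionnaire". For the remaining QuIC Part A analyses, the SAP says "The following non-primary analyses will use all randomized patients with possible exclusion of clinical trials protocols with high missing data rates", then "Non-primary analysis will rely on linear regression models with multiple imputations to address missing data issues". The Missing data paragraph plans multiple imputation with a tipping-point analysis, and specifies: "The imputation model will use the information at baseline when the participant is enrolled into the study". The note to Table 4 keeps the ETRIC term in the adjusted model whatever its significance.

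**Timing.** The SAP is dated 9/17/16. It reports that enrolment "closed in August 2016 when the targeted sample of 198 patients was enrolled", and that low questionnaire completion had already led to the larger sample size.

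**The concern.** The trial has one primary test, and its two governing documents give that test different populations. Whichever is used, the analysis departs from one of them, and the SAP neither says so nor gives a reason.

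The difference is about a third of the sample. Under Protocol 4.4.3 the QuIC may be taken home and mailed back, so return could be related to comprehension, which is what the test measures. If that relation differs by arm, comparing completers is biased, in either direction.

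The imputed analyses are the natural safeguard, but two features weaken it. They are non-primary for QuIC Part A. And the SAP lets them omit a whole parent protocol for high missingness, with no threshold, so the choice can be made after the completion pattern is seen. Omitting 0901 or 1203 would also go against Protocol 5.1. As written, no QuIC Part A analysis is certain to cover every randomized patient who had the parent-trial consent discussion.

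**Working it through.** **1. The plan's own figures.** Protocol 5.2 uses a 4-point difference, SD 8, two-sided 5% and 80% power. The exact t-test calculation gives 63.8, so 64 per group. Dividing by 0.864 for the Mann-Whitney test: 64/0.864 = 74.1, so 74 per group and 148 in total. With 25% dropout: 148/0.75 = 197.3, so 198. All three reproduce.

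**2. Size of the excluded group.** SAP expectation: 99 − 64 = 35 per arm, 35/99 = 35.4%, or 70 of 198. Protocol 5.2 allowed 99 − 74 = 25 per arm (25.3%).

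**3. Size of the exclusion option.** Appendix G gives about 19 patients from 0901 (19/198 = 9.6%) and about 100 from 1203 (100/198 = 50.5%). That leaves 198 − 19 − 100 = 79 (39.9%) for 1101 and 1301 together. Nothing in the documents says which protocol, if any, has high missingness.

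**4. Possible bias in the completer test.** Let k be the number per arm, out of the 35, who never had the consent discussion. The documents do not give k, so it is varied.

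- Non-return among those who had the discussion: f = (35 − k)/(99 − k).
- Let D be the difference between arms in the completer-minus-non-completer gap in mean score (assumed). With equal missingness, bias = f × D.
- SE of the completer difference = 8 × √(2/64) = 1.414.
- Type I error is from the noncentral t distribution with 126 df and noncentrality bias/1.414.

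| k | f | Bias, D = 4 | Type I, D = 4 | Type I, D = 2 | Type I, D = 1 |
|---|---|---|---|---|---|
| 0 | 35/99 = 35.4% | 1.41 | 16.8% | 7.9% | 5.7% |
| 18 | 17/81 = 21.0% | 0.84 | 9.1% | 6.0% | 5.3% |
| 25 | 10/74 = 13.5% | 0.54 | 6.7% | 5.4% | 5.1% |
| 35 | 0 | 0 | 5.0% | 5.0% | 5.0% |

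If missingness and the gaps are the same in both arms, the bias is zero for every k.

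**5. Tipping point.** The smallest significant difference is 1.979 × 1.414 = 2.80. If completers differ by 4 points, significance is lost when one arm's non-returners are shifted by (4 − 2.80)/f, about 3.4, 5.7 or 8.9 points for k = 0, 18 or 25 (approximate, since the completer SE is used). A shift applied equally to both arms changes the difference by shift × (f in ETRIC − f in standard), which is zero when non-return is equal. Only a shift that varies by arm is then informative.

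**6. What imputation can recover.** This is a simulation with no true effect, a gap of about 4 points in the ETRIC arm only, and 64 completers plus 35 non-returners per arm. It used 1,000 trials per setting, 20 imputations within arm, and assumed correlations with QuIC Part A of 0.3 for baseline data and 0.6 for the DICCT. Type I error was:

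- completers: 17.6%
- imputation from baseline data only: 14.5% to 15.7%
- with the DICCT added: 10.6%, or 12.9% if half of the non-returners also lack the DICCT

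The Monte Carlo standard error is about 1 percentage point. With 10 non-returners per arm, all methods were at about 5% to 7%. When return was unrelated to score and the true effect was 4 points, power was 79% to 80% for completers, 79% to 81% with baseline-only imputation and 81% to 84% with the DICCT.

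**The case against.** The strongest reply is that the departure is partly one of wording. Protocol 5.5 gives no route by which a patient without a score could enter an unadjusted t-test or Mann-Whitney test; its imputation text concerns regression. Protocol 5.2 inflates the sample so that enough scored patients remain, and the SAP is open about both the completer set and the low completion. This stands as a reason why a completer test may be defensible. It does not remove the conflict: sizing for evaluable patients sets recruitment and does not redefine the analysis set in 5.5.

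It can also be said that full coverage is the default, since SAP Tables 1 to 3 list all four parent protocols and the exclusion is only possible. That is fair. But an open option that could remove up to half the sample, and that sits against Protocol 5.1, should not stay undefined.

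Three stronger readings are tempting, and the documents support none of them:

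- **That the SAP ignores missing data.** It plans imputation and a tipping-point analysis. Its silence on arm-specific shifts is missing detail, not an error. The same holds for whether the literacy scores count as baseline: Protocol 5.4 lists them so, while 4.4.3 collects them after the discussion.
- **That the set was changed after seeing results by arm.** The documents report knowledge of completion rates and do not say whether scores by arm had been seen.
- **That all 35 per arm are wrongly left out.** Protocol 4.1 and 5.2 both anticipate patients who never reach the discussion. The form is unlikely to have caused that loss, and there is little sense in imputing comprehension of a discussion that did not take place.

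**Conclusion.** The contradiction over the primary analysis set is plain on the page and should be fixed, as should the exclusion clause with no threshold. Harm to the result is possible but not shown. It depends on non-return being related to comprehension differently in the two arms among patients who had the consent discussion, and the documents give no information on that. The top figure of 16.8% needs a differential gap as large as the trial's target effect and no loss at all before the discussion; a 1-point differential gives at most 5.7%. Both size and direction of any bias are unknown, and it may be zero. A reader should not infer that the completer result would be invalid, only that the plan does not yet fix its status or guarantee a full-coverage analysis to set beside it.

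**What to change.** 1. **One primary set.** Make Protocol 5.5 and the two SAP statements (Primary Endpoint and Data Analysis; Patients to Include) agree. If completers are kept, state this as a declared change from the protocol, with the reason.
2. **Delete the exclusion clause** for parent protocols with high missingness, so that the imputed QuIC Part A analysis covers all four, in line with Protocol 5.1. Any analysis that leaves one out is an additional sensitivity analysis only.
3. **Always report beside the completer test** the ETRIC-minus-standard QuIC Part A difference by multiple imputation within arm, for all randomized patients who had the parent-trial consent discussion, with the tipping-point shift varied separately by arm. Patients who did not have the discussion for any reason (ineligibility as in 4.1, or disease progression as in the 5.2 example) are counted by arm with the reason and not imputed.
4. **Strengthen the imputation model** with the observed DICCT score and the parent-trial consent decision.

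The cost is a SAP amendment and a clarifying sentence in Protocol 5.5. The DICCT and consent decision are already collected; reasons for missing the discussion depend on what sites recorded. The downsides are some added model dependence and analysis work, and imputation reduces but may not remove bias, which is why the arm-specific tipping-point analysis is needed with it.

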5.2. Sample Size and Power Calculations

Based on previous studies in the literature,^{4,43,44} this study is designed to detect a 4-point difference in the mean QuIC part A comprehension scores between the two study arms. This difference represents a 0.5 standard deviation difference and has been considered to represent a clinically meaningful difference in comprehension scores in previous studies. The sample size for a two-sample t-test will require 64 participants per group to detect a 4-unit difference between group means ($\alpha=5\%$, power=80%, standard deviation=8). Asymptotic relative efficiency of the Mann-Whitney test to the 2-sample t-test is 0.864 under any symmetric

distribution, which means that 15% more subjects will need to be recruited, leading to 74 per group or 148 in total. Another 25% is added to account for possible dropouts (e.g., patients consent for this study, but are subsequently not able to participate in the consent process for the BMT CTN parent clinical trial [e.g., due to disease progression or determined ineligible to participate]). The study will need to enroll 198 subjects (approximately 99 in each arm). The stratified randomization will eliminate possible association between trial and center strata and consent group assignment, which potentially increases power properties.

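### The primary analysis of a mean can switch to a Mann-Whitney test on an unspecified check of the data; one test of the mean difference should be fixed before any analysis by arm

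*SAP*

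**What the plan says.** The SAP (Primary Endpoint and Data Analysis) states that the primary endpoint "is the mean comprehension score on the Quality of Informed Consent (part A) instrument". The analysis "will be based on the two sample t-test or, if the t-test assumptions are violated, with Mann-Whitney test". The decision rule is "The statistical significance will be declared if the P-values of a two-sided test <0.05".

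Protocol 5.5 has a similar rule: "The t-test or the Mann-Whitney test will be used if the t-test assumptions are violated". Read literally, that sentence offers either test once an assumption fails. The intended meaning is presumably the SAP's.

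Protocol 5.2 says that "this study is designed to detect a 4-point difference in the mean QuIC part A comprehension scores between the two study arms". It derives 64 per arm for the t-test, then raises this to 74 per arm because "Asymptotic relative efficiency of the Mann-Whitney test to the 2-sample t-test is 0.864 under any symmetric" distribution, and then to 198 in total for 25% dropout. The SAP's Protocol Synopsis keeps 198 enrolled but expects 64 completers of QuIC-A per arm. Its Missing data paragraph expects about two thirds to complete, which is 66 of 99.

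Neither document says which assumption is checked, by what method, at what threshold, by whom, or whether blind to arm. The SAP's Alternative analyses paragraph mentions non-normal residuals and outliers, but for the regression models and without a threshold.

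**The concern.** The two tests answer different questions. The t-test compares means, which is what the endpoint and the 4-point design difference concern. Mann-Whitney compares the distributions through ranks, and matches a comparison of means only under extra conditions such as a pure shift. So an undefined look at the outcome data decides which hypothesis the primary p-value addresses.

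The trigger is likely to matter. QuIC-A has 16 three-option items normalized to 0-100 (Protocol 4.4.2), so scores are discrete and bounded and cannot be exactly normal. Equal variance is also an assumption of the ordinary t-test. A reader could therefore take unequal spread as grounds for Mann-Whitney, and that is a case in which it can fail as a test of means. Two analysts following the plan in good faith could report different primary p-values.

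**Working it through.** **1. The plan's sample size reproduces.** Inputs from Protocol 5.2: difference 4, SD 8 (so d = 4/8 = 0.5), two-sided alpha 0.05, power 80%.

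- t-test: the noncentral t solution is 63.8, so 64 per arm.
- Mann-Whitney: 64/0.864 = 74.07, so 74 per arm and 148 in total.
- Dropout: 148/(1 − 0.25) = 197.3, so 198.

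**2. Power at the completers the SAP expects.** Noncentral t power at d = 0.5, with the effective n for Mann-Whitney taken as n × 0.864.

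| Completers per arm | t-test | Mann-Whitney: effective n | Mann-Whitney: power |
|---|---|---|---|
| 64 | 80.1% | 64 × 0.864 = 55.3 | 74.1% |
| 66 | 81.4% | 66 × 0.864 = 57.0 | 75.4% |
| 74 | 85.6% | 74 × 0.864 = 63.9 | 80.1% |

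The 64 completers cover the t-test only. An efficiency of 0.955 (normal data, assumed) gives Mann-Whitney 78.3% at 64.

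**3. Does the t-test need rescuing?** The documents give no score distribution, so shapes are assumed: normal, bounded with mean 80 or 90, discrete, and strongly skewed. With 20,000 trials per setting at 64 and 66 per arm, and the same distribution in both arms, type I error was 4.7% to 5.4% for both the pooled and the Welch t-test.

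The pooled version is weaker if spreads and completer numbers both differ. With equal means of 80, SD 6 in 76 completers and SD 12 in 54, it rejected in 8.2% of trials. With SD 6 in 54 and SD 12 in 76, it rejected in 3.2%. Welch gave 5.2% and 5.1%.

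**4. What Mann-Whitney tests when spreads differ.** Equal means of 80, SDs of 6 and 12, 66 per arm, bounded scores: Mann-Whitney rejected in 15.2% of trials, Welch in 5.0%. A separate run with skewed scores gave 21% against 4.9%. The excess needs skew as well as unequal spread. In a check with the same means, SDs and numbers (10,000 trials), Mann-Whitney rejected in 5.2% of trials for normal scores, 11% at skew 0.8 and 22% at skew 1.3.

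**5. Type I error of the choice itself.** If the smaller p-value were always reported, it would be 5.5% to 7.2% across the settings tried. If a fixed Shapiro-Wilk test made the choice, it would be 4.5% to 5.9%.

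**6. How often the choice matters under a true effect.** At 64 per arm, SD 8 and a 4-point shift, the verdicts differed in 5.1% of trials (normal), 5.7% (bounded, mean 80) and 12.1% (bounded, mean 90). In the last case the t-test rejected in 80.3%, Mann-Whitney in 91.9%, and at least one in 92.2%. Mann-Whitney alone therefore rejected in 92.2 − 80.3 = 11.9%, and the t-test alone in 92.2 − 91.9 = 0.3%. Under skew, the disagreement is mostly Mann-Whitney finding a real shift.

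**The case against.** The strongest reply is that the fallback is neither improvised nor unbudgeted: Protocol 5.5 specifies it and 5.2 pays for it. That stands. What remains is the missing trigger, the change of hypothesis, and the fall from 74 to 64 expected completers.

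The reply on power also stands. At assumed skew 1.3 with a pure shift, Mann-Whitney has about 90% power against 80% at 4 points, and 70% against 57% at 3 points. A score bounded at 100 may well be skewed. The simulated shifts were not capped at 100, however, so near the ceiling a pure shift is only an approximation. The case for Welch rests on fixing what is tested, not on power.

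An arm-blind trigger, or Mann-Whitney fixed as primary, would also remove the ambiguity. The first would still let the hypothesis vary. The second would need the endpoint redefined and would have about 74% power at the planned efficiency.

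Four stronger readings are tempting, and the documents do not support them.

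- **That the test was left open to suit the result**, because the SAP is dated September 2016 and enrolment closed in August. The SAP repeats a rule already in the protocol, and the only earlier data look it describes concerned survey completion.
- **That the plan carries a 7% type I error.** That needs a smaller-p rule, whereas both documents tie the switch to assumptions.
- **That a Mann-Whitney result would leave no inference on the mean.** SAP Table 2 reports means with standard errors by arm, and Table 4 reports an ETRIC coefficient with its p-value, although that analysis is adjusted and non-primary.
- **That any t-test would be valid.** The pooled version may not be if spreads and completer numbers both differ.

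**Conclusion.** The concern holds as a gap in the primary analysis rule. An unspecified check decides whether the primary p-value tests the mean difference the trial was designed to detect or something else. The switch is not needed for validity, since Welch holds about 5% at 64 per arm under the skew tried.

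Its size is moderate. At 64 completers the fallback has about 74% power against 80%, using the protocol's efficiency. With skewed scores and a twofold difference in SD it rejects equal means in about 15% to 21% of trials. The type I error cost of a fixed normality trigger is small, and 5.5% to 7% is a worst case.

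The design SD of 8 and the 0-100 scale come from the protocol. Score shapes, mean levels, unequal SDs and unequal completer numbers are assumptions.

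**What to change.** Before any analysis by arm, replace the SAP's rule with:

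> The primary analysis is a two-sided unequal-variance (Welch) t-test of the difference in mean QuIC-A score, reported with a 95% CI; the Mann-Whitney test is a sensitivity analysis.

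Replace the whole corresponding sentence in Protocol 5.5 with the same text, or state in the SAP that it supersedes that sentence. Deleting only the conditional clause from the protocol would leave an unconditional choice between the two tests, which is worse than the present wording.

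No extra patients or data are needed: power at 4 points and SD 8 is 80.1% with 64 completers per arm. The costs are wording in two documents and, if scores are strongly skewed and the effect is a pure shift, the loss of power against Mann-Whitney given above.
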